OBJECTIVES: The objective of this study is to evaluate the safety and hemostatic effectiveness of EVARREST Fibrin Sealant Patch (EVARREST) in controlling mild or moderate soft tissue & parenchymal bleeding during open hepatic, abdominal, pelvic, retroperitoneal, and thoracic (non-cardiac) surgery in pediatric patients.

STUDY DESIGN: This is an open label, prospective, multicenter, single arm clinical study evaluating EVARREST as an adjunct to hemostasis when conventional methods (i.e. suture, ligature, cautery) of controlling mild or moderate bleeding are ineffective or impractical during surgery in pediatric patients.

For this study, approximately 12 sites in US and UK will be utilized for consecutive screening and enrollment.

At least thirty-five (35) pediatric subjects with an appropriate mild or moderate bleeding TBS will be enrolled in this study. The age of the subjects enrolled in the study will be from 1 month to <18 years. This will include a minimum of 4 subjects aged 1 month (≥ 28 days from birth) to <1 year.

All subjects will be followed post-operatively through hospital discharge and at 30 days (+/-14 days) post-surgery.

TBS DEFINITION: The **Target Bleeding Site (TBS)** will be defined as the first accessible mild or moderate bleeding site identified in the hepatic parenchyma or soft tissue, where conventional methods of controlling bleeding are ineffective or impractical and is amenable to manual compression. The TBS must be a site where occlusion of the injured tissue surface blood vessels is required to achieve hemostasis.

The TBS must be an area that can have firm pressure applied and maintained continuously until 4 minutes after TBS identification, and to which EVARREST can be applied with a margin of 0.5-1 inch (1-2 cm). (Refer to Investigator's Brochure).

EVARREST should not be used on large defects in arteries or veins where the injured vascular wall requires repair with maintenance of vessel patency and which would result in persistent exposure of the EVARREST to blood flow and pressure during healing and absorption of the product. EVARREST should not be used in place of sutures or other forms of mechanical ligation for the primary treatment of major arterial bleeding.

Mild Bleeding: a TBS with a small area of capillary, arteriole or venule oozing

Moderate Bleeding: A TBS with a larger area of capillary, arteriole, or venule oozing that presents a significant challenge because of the larger area involved, increasing the volume of blood loss, or a TBS with bleeding that is more pronounced than oozing, that could also come from a small artery or vein, but is not massive.

Severe Bleeding (EXCLUDED FROM THIS PROTOCOL): (arterial, venous, or mixed) that is rapidly flowing, pulsatile or spurting that in the surgeon's judgment requires rapid control to prevent hemodynamic consequences (e.g. hypovolemia, tachycardia, or hypotension) and could involve major volume loss which if not treated rapidly could be life threatening. EVARREST should not be used in place of sutures or other forms of mechanical ligation for the treatment of major arterial bleeding.

PROCEDURE: For this study, the TBS will be defined as the FIRST actively bleeding site identified during the soft tissue or hepatic dissection related to the primary operative procedure with challenging mild to moderate bleeding. This site will then be assessed for hemostatic effectiveness after product application as described below.

Once the TBS is identified, the surgeon will immediately apply EVARREST at the actively bleeding TBS. The size of the treatment article applied should be sufficient for coverage of the entire TBS and should overlap the bleeding source with a margin of 0.5-1 inch (1-2cm).

After placement of EVARREST, **the surgeon will apply** firm continual manual compression over the entire bleeding area until 4 minutes from TBS identification. The surgeon may use a surgical sponge (laparotomy pad or surgical gauze) to assist in providing adequate pressure over the entire surface area.

Hemostasis is defined as no detectable bleeding at the TBS. Absolute time to hemostasis, defined as the absolute time elapsed from TBS identification to the last moment in time at which detectable bleeding at the TBS is observed, will be recorded.

Hemostasis will be assessed at 4 minutes from TBS identification by carefully releasing manual compression and removing the surgical sponge (if used). Hemostasis will also be assessed at 10 minutes from TBS identification and absolute time to hemostasis will be recorded.

EVARREST should not be removed after bleeding has been stopped.

If bleeding requiring treatment occurs after the 4 minute assessment the surgeon can retreat the TBS with EVARREST or revert to their standard of care.

Additional Treatment Impact on the Success/Failure of Endpoints

- Any additional treatment at the TBS after the 4 minute endpoint will be considered a failure for the 4 minute secondary endpoint.
- Any additional treatment after the 10 minute time point will be considered a failure for the 10 minutes secondary endpoint.

Any EVARREST re-treatment must be performed according to the Investigator's Brochure.

Hemostasis will be assessed at 4 minutes and 10 minutes after TBS identification

and absolute time to hemostasis is recorded regardless of any additional treatments.

EVARREST can only be used on a single TBS to be evaluated. If additional soft tissue or hepatic parenchymal bleeding sites are identified, the surgeon should treat according to their standard of care.

TEST PRODUCT: EVARREST Fibrin Sealant Patch

STUDY

POPULATION: Pediatric subjects, undergoing non-emergent abdominal, retroperitoneal, pelvic, hepatic or thoracic (non-cardiac) surgery procedures, wherein an appropriate TBS is identified. For this study, pediatric subjects are defined as:

Infants and toddlers (28 days (1 month) from birth to 23 months), children (2 to 11 years) and adolescents (12 to less than 18 years). A minimum of 4 subjects aged 1 month (≥ 28 days from birth) to <1 year will be enrolled in this study.

Newborn infants (0-27 days from birth) are excluded from this study. Pre-term births are excluded from this protocol until the subject reaches 28 days from 37 weeks of pregnancy as determined by the investigator.

PRIMARY

ENDPOINT: Absolute time to hemostasis defined as the absolute time elapsed from TBS identification to the last moment in time at which detectable bleeding at the TBS is observed.

SECONDARY

ENDPOINTS:

- Proportion of subjects achieving hemostatic success at 4 minutes following TBS identification and no bleeding requiring treatment at the TBS any time prior to final fascial closure
- Proportion of subjects achieving hemostatic success at 10 minutes following TBS identification and no bleeding requiring treatment at the TBS any time prior to final fascial closure
- Proportion of subjects with no re-bleeding at the TBS
- Incidence of adverse events that are potentially related to bleeding at the TBS;
- Incidence of adverse events that are potentially related to thrombotic events;
- Incidence of re-treatment at the TBS;
- Incidence of any adverse events
- Summarization of hemoglobin, hematocrit, platelets, laboratory results, estimated intraoperative blood loss and number of blood products transfusions

SAFETY: Adverse events will be collected from time of TBS identification, throughout the follow-up period. Intra-operative bleeding at the TBS after 10 minutes will be considered an adverse event.

The following data will also be collected: laboratory tests (including hemoglobin, hematocrit, platelets), estimated intraoperative blood loss and number of blood products transfused.

STATISTICAL ANALYSIS:

Sample size of 35 subjects is considered adequate to summarize data descriptively. The continuous data will be summarized by number of subjects, mean, median and standard deviation (SD). The categorical data will be summarized by frequency along with associated percentages. A two-sided 95% confidence interval (CI) for median absolute time to hemostasis will be reported. In addition, for success/failure secondary endpoints (4 and 10 minutes hemostasis endpoints), two-sided 95% CI will be reported for P_F , where P_F is the proportion of success in EVARREST subjects. The lower limits of these 95% CI will be utilized for statistical inferences.

SAMPLE SIZE: At least 35 qualified subjects with an identified TBS.

SURGICAL PROCEDURES:

Open surgical procedures with challenging mild or moderate hepatic parenchyma or soft tissue target bleeding sites.

The surgical procedures must be open procedures, to allow for appropriate EVARREST application. When patients are undergoing abdominal and thoracic (non-cardiac) procedures, open is defined as the opening of the peritoneal or pleural/thoracic cavity. The following surgical procedures are permitted to be included in this study:

- Hepatic
- Intra-Abdominal
- Intra-Thoracic (Non-Cardiac)
- Retroperitoneal
- Pelvic (Extra-peritoneal space)

Laparoscopic, thoracoscopic and other endoscopic procedures are excluded from this study.

Soft Tissue includes but may not be limited to the following tissue types:

- Muscle
- Lymphatic Tissue/lymph node beds
- Fatty tissue
- Loose Areolar Connective Tissue
- Other tissue types (specify) excluding visceral organs except liver

The study will target to have a minimum of 20 procedures with the target bleeding site in the hepatic parenchyma and the remaining procedures with the target bleeding sites in soft tissue. Enrollment will be monitored by the Sponsor and the Investigators will be notified by the Sponsor once those targets have been met.

Inclusion Criteria*Pre-operative:*

1. Pediatric subjects aged ≥ 28 days (≥ 1 month) to < 18 years, requiring non-emergent open hepatic, abdominal, retroperitoneal, pelvic or thoracic (non-cardiac) surgical procedures;
 - i) A minimum of 4 subjects to be enrolled aged ≥ 28 days to < 1 year.
2. The subject's parent/legal guardian must be willing to give permission for the subject to participate in the trial and provide written Informed Consent for the subject. In addition, assent must be obtained from pediatric subjects who possess the intellectual and emotional ability to comprehend the concepts involved in the trial. If the pediatric subject is not able to provide assent (due to age, maturity and/or inability to intellectually and/or emotionally comprehend the trial), the parent/legal guardian's written Informed Consent for the subject will be acceptable for the subject to be included in the study.

Intra-operative

3. Presence of an appropriate mild or moderate bleeding soft tissue or hepatic parenchyma TBS identified intra-operatively by the surgeon;
4. Ability to firmly press trial treatment at TBS until 4 minutes after TBS identification;

Exclusion Criteria*Pre-operative*

1. Subjects with known intolerance to blood products or to one of the components of the study product or is unwilling to receive blood products;
2. Female subjects, who are of childbearing age (i.e. adolescent), who are pregnant or nursing;
3. Subject is currently participating or plans to participate in any other investigational device or drug study during this study period without prior approval from the Sponsor;
4. Subjects who are known current alcohol and/or drug abusers
5. Subjects admitted for trauma surgery
6. Subjects with any pre or intra-operative findings identified by the surgeon that may preclude conduct of the study procedure.
7. Subjects that have received a COVID-19 vaccine either 4 weeks prior to surgery or scheduled to receive COVID-19 vaccine within the 30-day follow-up period.

Intra-operative

8. Subject with TBS in an actively infected field (Class III Contaminated or Class IV Dirty or Infected)¹
9. TBS is from large defects in arteries or veins where the injured vascular wall requires repair with maintenance of vessel patency and which would result in persistent exposure of EVARREST to blood flow and pressure during healing and absorption of the product;
10. TBS with major arterial bleeding requiring suture or mechanical ligation;
11. Bleeding site is in, around, or in proximity to foramina in bone, or areas of bony confine.

¹ Appendix 1

SCHEDULE OF EVENTS

Procedures	Screening (within 21 days prior to procedure)⁴	Baseline (within 24 hours prior to procedure)	Surgical Procedure	Post- Surgery to Hospital Discharge	30-Day Follow Up (+/- 14 days)⁵
Inclusion/ Exclusion	X	X	X		
Informed Consent / Assent (as applicable)	X				
Demographics	X				
Medical and Surgical History	X	X¹			
Concomitant Medications		X	X	X	X
Physical Exam (including height and weight)	X			X	
Complete Blood Count with Differential	X²	X²		X	
Coagulation (PT, aPTT, INR)	X²	X²		X	
Pregnancy Tests (if applicable)		X			
Treatment Application and Hemostasis assessment			X		
Determination of Hemostasis at TBS			X		
Operative/Surgical information ³			X	X	
Assessment of bleeding or thrombotic events			X	X	X
Adverse Events			X	X	X

¹ Review for changes in medical history from screening visit and preform pregnancy test (if applicable)² At least one CBC with differential and coagulation parameter are needed pre-procedure. If pre-operative blood tests are repeated, the blood test closest to the date prior to surgery will be used.³ Including length of stay, blood loss and transfusion information.⁴ May be combined with Baseline visit⁵ May be conducted via telephone if clinic visit not possible

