The analysis (all randomized subjects) for the primary effectiveness endpoint demonstrated that the median absolute time taken to achieve hemostasis in both groups was 4.0 minutes (95% CI of median: [4.0, 4.0 minutes] in EVARREST group; [4.0, 7.6 minutes] in SURGICEL® group). The primary effectiveness endpoint was also analyzed by age group (28 days to <24 months, 2 to 11 years, and 12 to <18 years), and the median absolute time to hemostasis was 4.0 minutes among all the age groups in both EVARREST and SURGICEL® groups. The percentage of subjects with hemostasis at 4 minutes following randomization was higher in EVARREST group (80.0%, 16/20 subjects, 95% CI: 56.3-94.3%) compared to SURGICEL® group (60.0%, 12/20 subjects, 95% CI: 36.1-80.9%); the ratio of proportions (EVARREST/SURGICEL®) was 1.33 (95% CI: [0.87, 2.16]). A higher percentage of subjects achieving hemostasis at 10 minutes following randomization was also observed in the EVARREST group (95.0%, 19/20 subjects, 95% CI: [75.1%, 99.9%]) compared to the SURGICEL® group (90.0%, 18/20 subjects, 95% CI: [68.3%, 98.8%]). In addition, the surgeon reverted to standard of care for 3 subjects in the SURGICEL group achieving hemostasis at the 10-minute time point assessment.

No new safety signals were identified in this study. The AE and SAE profiles in this study are those that would be anticipated following major surgical procedures in the population treated. No clinically meaningful differences between treatment groups were observed, and all SAEs that occurred were single events.

EVARREST Fibrin Sealant Patch was first approved in the US in 2012 (BLA # 1603) and is currently indicated for use with manual compression as an adjunct to hemostasis in adult patients undergoing surgery, when control of bleeding by standard surgical methods of hemostasis (e.g., suture, ligature, cautery) is ineffective or impractical.

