If breakthrough bleeding occurs at the TBS at any time after application, the surgeon may re-treat with EVARREST if clinically appropriate, or revert to their standard of care. Any EVARREST re-treatment must be performed according to the Investigator's Brochure.

EVARREST Re-treatment

- If the surgeon finds the EVARREST was not applied properly (if there are folds, creases or crimps in the patch) the EVARREST patch may be removed in its entirety and a new EVARREST applied as per the Investigator's Brochure. No matter the point of application, hemostasis must be assessed at 4 and 10 minutes from TBS identification.
- If bleeding is due to insufficient coverage of the bleeding area, additional patches may be applied. Ensure that the edges overlap (by approximately 0.5 to 1 inch or 1 to 2 cm) with the existing patch.
- If bleeding is due to incomplete adherence to the tissue (where bleeding persists under the dressing), remove the patch and use a new one.
- If bleeding still occurs during or after the specified duration of compression, remove the used EVARREST and inspect the bleeding site. If no other primary hemostatic measures (i.e., standard surgical techniques) appear to be required, repeat the application procedure above with a new EVARREST.

EVARREST can only be used on the single TBS to be evaluated. If additional soft tissue/hepatic bleeding sites are identified, the surgeon should treat according to their standard of care.

HEMOSTASIS ASSESSMENT (TIMETABLE):

T₀	Start time when the first appropriate TBS is identified.
T_{APP}	Time when hemostatic product is initially applied with manual compression.
T₄	TBS Bleeding assessment 4 minutes following TBS identification. Note: Manual compression must be maintained from application until this initial assessment.
T₁₀	TBS Bleeding assessment 10 minutes following TBS identification.
T_{ABS}	Absolute time to hemostasis; as defined as the absolute time elapsed from TBS identification to the last moment in time at which there is detectable bleeding at the TBS.

- 7.1.3.1 Adverse events from start of TBS identification, including any complications potentially related to bleeding and/or thrombotic events.

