After placement of EVARREST, the surgeon will apply firm continual manual compression over the entire bleeding area until 4 minutes from TBS identification. The surgeon may use a surgical sponge (laparotomy pad or surgical gauze) to assist in providing adequate pressure over the entire surface area.

Hemostasis is defined as no detectable bleeding at the TBS. Absolute time to hemostasis, defined as the absolute time elapsed from TBS identification to the last moment in time at which detectable bleeding at the TBS is observed, will be recorded.

Hemostasis will be assessed at 4 minutes from TBS identification by carefully releasing manual compression and removing the surgical sponge (if used). Hemostasis will also be assessed at 10 minutes from TBS identification and at initiation of final fascial closure. The absolute time to hemostasis will be recorded. EVARREST should not be removed after bleeding has been stopped.

If bleeding requiring treatment occurs after the 4 minute assessment, the surgeon can retreat the TBS with EVARREST or revert to their standard of care.

Hemostasis will be assessed at 4 minutes and 10 minutes after TBS identification and absolute time to hemostasis is recorded regardless of any additional treatments.

EVARREST can only be used on a single TBS to be evaluated. If additional soft tissue or hepatic parenchymal bleeding sites are identified, the surgeon should treat according to their standard of care.

Primary Endpoint:

The primary endpoint in this study will be the absolute time to hemostasis defined as the absolute time elapsed from TBS identification to the last moment in time at which detectable bleeding at the TBS is observed.

Secondary Endpoints:

- Proportion of subjects achieving hemostatic success at 4 minutes following TBS identification and no bleeding requiring treatment at the TBS any time prior to final fascial closure
- Proportion of subjects achieving hemostatic success at 10 minutes following TBS identification and no bleeding requiring treatment at the TBS any time prior to final fascial closure
- Proportion of subjects with no re-bleeding at the TBS

Safety Endpoints:

- Incidence of adverse events that are potentially related to bleeding at the TBS
- Incidence of adverse events that are potentially related to thrombotic events
- Incidence of re-treatment at the TBS
- Incidence of any adverse events, which will be collected from time of TBS identification, throughout the follow-up period

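### The plan does not settle how a subject given additional treatment between 4 and 10 minutes is scored at 10 minutes, and one reading credits standard-of-care hemostasis to EVARREST

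*Protocol*

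**What the plan says.** The synopsis, under Additional Treatment Impact on the Success/Failure of Endpoints, has two bullets. For the 4-minute endpoint: "Any additional treatment at the TBS after the 4 minute endpoint will be considered a failure for the 4 minute secondary endpoint". For the 10-minute endpoint: "Any additional treatment after the 10 minute time point will be considered a failure for the 10 minutes secondary endpoint". Neither bullet appears in protocol 8.3 or in the SAP.

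The synopsis defines the 10-minute secondary endpoint as "hemostatic success at 10 minutes following TBS identification and no bleeding requiring treatment at the TBS any time prior to final fascial closure". Protocol sections 2 and 8.3.1 and SAP section 1 carry essentially the same definition. SAP 9.4.2 plans counts, percentages and a Clopper-Pearson interval, but does not say how a subject is classified.

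Treatment between the two assessments is allowed. The synopsis procedure says: "If bleeding requiring treatment occurs after the 4 minute assessment the surgeon can retreat the TBS with EVARREST or revert to their standard of care". Protocol 7.1.3 is wider: "If breakthrough bleeding occurs at the TBS at any time after application, the surgeon may re-treat with EVARREST if clinically appropriate", with standard of care as the alternative. Hemostasis is still assessed at 10 minutes whatever was done in between.

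**The concern.** Take a subject who is bleeding at 4 minutes, is switched to standard of care at 5 minutes, is dry (no detectable bleeding) at 10 minutes and needs nothing more. The second bullet fails only treatment given after 10 minutes, so by contrast with the first it implies that this subject can be a 10-minute success. The definition sets no start time for its ban on bleeding that requires treatment, so read literally it makes the subject a failure.

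The trial has one arm. If such subjects count as successes, hemostasis obtained by another method enters the product's 10-minute rate and no control rate offsets it. The trial is also open-label, so leaving the rule open until results are visible allows the choice to follow the data.

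There is a smaller gap before 4 minutes. Section 7.1.3 allows re-treatment at any time after application, but neither bullet scores treatment given before the 4-minute assessment.

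**Working it through.** **Step 1: the texts applied to one subject** (treated between 4 and 10 minutes, dry at 10 minutes, no later treatment).

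| Text | 4-minute endpoint | 10-minute endpoint |
|---|---|---|
| Synopsis bullets | Failure | Not stated; success implied |
| Definition, read literally | Failure | Failure |
| Definition, read as running from the assessment onward | Failure | Success |

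The plan therefore either conflicts with itself or counts rescue as product success.

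**Step 2: can the case arise?** The introduction reports on the previous pediatric trial that "the surgeon reverted to standard of care for 3 subjects in the SURGICEL group achieving hemostasis at the 10-minute time point assessment". So it did arise, in the comparator arm, and the wording suggests that those subjects were counted as 10-minute successes. No matching count is given for EVARREST.

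**Step 3: reproduce the documents' intervals.** Clopper-Pearson 95% limits for x successes in n: lower = Beta quantile (0.025; x, n−x+1), upper = Beta quantile (0.975; x+1, n−x). For the previous trial:

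- 16/20: 56.3-94.3%
- 19/20: 75.1-99.9%
- 12/20: 36.1-80.9%
- 18/20: 68.3-98.8%

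All four match the introduction.

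**Step 4: effect at n = 35.** Assumption: the previous EVARREST 10-minute rate carries over, 0.95 × 35 = 33.25, taken as 33 dry at 10 minutes. Let k of these have had additional treatment between 4 and 10 minutes. Counting them as failures gives x = 33 − k.

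| k | x/35 | Rate | 95% CI |
|---|---|---|---|
| 0 | 33/35 | 94.3% | 80.8-99.3 |
| 1 | 32/35 | 91.4% | 76.9-98.2 |
| 2 | 31/35 | 88.6% | 73.3-96.8 |
| 3 | 30/35 | 85.7% | 69.7-95.2 |
| 4 | 29/35 | 82.9% | 66.4-93.4 |
| 5 | 28/35 | 80.0% | 63.1-91.6 |

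Each such subject moves the rate by 1/35 = 2.9 points. The top of the range, k = 5, is illustrative. The previous trial had 19 − 16 = 3 more EVARREST successes at 10 minutes than at 4 minutes, and 3/20 × 35 = 5.25. So k = 5 supposes that all late successes had additional treatment.

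**Step 5: the one documented count.** If the 3 comparator subjects are among that arm's 18 successes, the literal definition gives 15/20 = 75.0% (50.9-91.3) instead of 90.0%. This shows how far the two scorings can part. It does not estimate anything for EVARREST.

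**The case against.** A reader might infer that the plan declares these subjects successes and so inflates the 10-minute rate. The documents do not support that. The second bullet is silent on treatment between 4 and 10 minutes, so success is implied by contrast and not stated. Bullets and definition can also be applied together, so that failing either fails the endpoint. Or the definition can be read in sequence: dry at 10 minutes, then no bleeding requiring treatment until closure. The sequential reading removes the contradiction and gives the 10-minute endpoint a clearer purpose of its own. It does not cure the problem, because rescue with standard of care then counts as product success.

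A reader might also infer a clash between protocol and SAP. Both carry the same definition. The tension lies within the protocol synopsis, and the SAP merely fails to resolve it.

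Nor do the documents show that the no-re-bleeding endpoint must count rescued subjects as successes. A rescued subject who becomes dry can bleed again, and no scoring for that endpoint is given.

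Other points stand. Additional treatment may be a second EVARREST patch, which is not hemostasis by another method. The endpoint is secondary, with no hypothesis test. SAP section 6 calls all intervals descriptive, although the synopsis says that their lower limits will be used for inference. Additional treatment is partly visible already: time to hemostasis is summarized with and without it (protocol 8.3.1, SAP 9.4.1), and re-treatment incidence is reported. Neither output shows the 10-minute proportion by type of treatment.

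**Conclusion.** The point holds as an unresolved scoring rule. For a foreseeable subject, the synopsis bullet implies one result and the literal definition gives the other. The reading that reconciles them credits standard-of-care hemostasis to EVARREST.

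On the assumption of 33/35 dry at 10 minutes, the gap between the two scorings runs from 0 points (k = 0) to 14.3 points (k = 5), and the lower confidence limit runs from 80.8% to 63.1%. The documents do not place EVARREST within that range. The primary endpoint is untouched. This should be fixed, but it does not undermine the trial.

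**What to change.** Replace the two synopsis bullets and put one rule in SAP 9.4.2 that matches the definition. Any additional treatment for bleeding at the target bleeding site between T0 and final fascial closure is a failure for both the 4-minute and the 10-minute endpoint. This includes treatment before 4 minutes and between 4 and 10 minutes.

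As a separate descriptive row, report hemostasis at 10 minutes regardless of additional treatment, split into:

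- no additional treatment
- EVARREST re-treatment only
- any other hemostatic method

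The synopsis procedure and section 7.1.3 differ on when re-treatment may occur and must be reconciled.

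The cost is mainly wording, settled before database lock. The 10-minute rate may come out lower. Section 7.1.3.2 already records additional methods, but neither it nor the assessment timetable names a time for them, so the eCRF may need such a field to support the split.
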